D.3.a. Framingham Risk Score. FRS (64) is calculated using age, gender, blood pressure, total and HDL cholesterol, smoking status, diabetes status, and status of taking blood pressure medication; we are excluding diabetic patients (see D.3.a.ii below). As such, all patients in the study will have hypertension with less-than-optimal control, **OR** elevated total cholesterol, **OR** be a current smoker. The table shows some typical FRS risk profiles. The examples are all male non-smokers:

	Subject A1	Subject A2	Subject B1	Subject B2	Subject C1	Subject C2	
Age	50	50	55	55	55	55	
SBP (on med)	-	-	-	-	140	-	
SBP (no med)	135	135	160	140	-	140	
Total cholesterol	210	190	190	190	190	190	
HDL	35	45	45	45	45	45	
10 yr FRS	7%	5%	9%	7%	9%	7%	

D.3.b. Rationale for 5% risk, with 2% reversibility. We are targeting a group of primary prevention patients that are relatively sick for primary prevention. A 2% reversibility is chosen because this is approximately the effect size seen in our study of a similar intervention among non-VA users; 5% baseline risk is chosen because patients with lower risk than this likely will not justify this relatively intensive intervention (nor, often, have 2% reversibility).

D.3.c. Process for identifying eligible patients. We will use a multi-phase process to identify patients that fit this demographic, reviewing aggregated local CPRS data first, then reviewing individual charts, then interviewing patients and obtaining lab data. We will target enrolling 200 from each site (Durham and Buffalo).

D.3.c.i Accrual of potential eligible patients from database: Patients will be initially identified from local VA administrative data (or VINCI, depending on VA policy at that time). In the database phase, identification will use the following inclusion and exclusion criteria:

 Inclusion: a diagnosis of inadequately controlled hypertension, as defined by an outpatient ICD-9 code of 401.x and a most recent blood pressure with either systolic > 140 mmHg or diastolic > 90 mmHg, **OR** (2) inadequately controlled dyslipidemia, as defined by most recent total cholesterol > 200 mg/dl **or** HDL cholesterol < 35 mg/dl, **OR** (3) current smoking, which can be identified using the CPRS Health Factor tied to the smoking clinical reminder. Medication-taking status for these illnesses is neither required nor excluded.

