D.9.b. Missing Data. Because the main predictors of interest, intervention arm and demographics, are collected at baseline, we do not anticipate much missing data in these variables. There may be missing values in the outcome measures due to drop-out, a missed interim assessment, or item non-response. Given a thorough understanding of the missing data mechanism, it is possible to use all of the available information in analysis, rather than using only subjects with completely observed information. Our main analysis technique, general linear mixed models via maximum likelihood estimation, implicitly accommodates missingness when missingness is due either to treatment, to prior outcome, or to other baseline covariates included in the model (81), defined as missing at random (MAR). Therefore, inferences will be valid even if we have differential dropout by intervention arm. If the missing values are related to other measured patient factors, such as age, gender, or employment status, then multiple imputation (MI) provides a framework for being able to incorporate information from these auxiliary variables while still preserving a parsimonious main treatment effect model (82) and is described as a significant advantage in recommendations from Panel on Handling Missing Data in Clinical Trials (2010) (83). Depending on the type and scope of missing data MI will be conducted via the SAS procedure PROC MI or the SAS macro IVEware (http://www.isr.umich.edu/src/smp/ive/) (84). If the probability of dropout is related to the actual missing response (which is unobserved because it is missing) or to other unobserved quantities, the missing data due to dropout is considered missing not at random (MNAR) or nonignorable (85). There is a possibility that data may be MNAR, and we propose as additional sensitivity analyses to explore MNAR methods, including selection and pattern-mixture models as recommended by Molenberghs and Kenward (86).

D.9.c. Intent-to-Treat Analysis. All of the proposed primary and secondary analyses focus on the effect of GPC as compared to usual care. We, therefore, plan to use the intent-to-treat assumption for all analyses.

D.9.d. Primary Analysis. The GPC vs usual care comparison in Framingham risk score change from baseline to month 6 will be examined with the following general linear mixed model,

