 $Y_{ijt} = \beta_0 + \beta_1 int^* month6 + \beta_2 month12 + \beta_3 int^* month12 + \beta_4 site + \beta_5 gender + \beta_6 smoking + c_j int^* month6,$

where Y_{ijt} is Framingham risk score for subject *i* in group *j* at *t*=month0, month6. We will estimate the parameters in the model using the SAS procedure MIXED (Cary, NC), and we will test to see if there is a difference in mean FRS change at month 6 between the GPC and usual care arm, i.e., $\beta_1 < 0$. The way time is coded in this model is often referred to as a constrained longitudinal data model (cLDA) (87) in which the month 0 risk is modeled as a dependent variable in conjunction with the constraint of a common month0 mean across the treatment arms. In this way, the cLDA model is comparable to an ANCOVA model; the two models are equivalent when there is no missing data. However, unlike an ANCOVA, subjects who are missing the month 6 measurement are included in the model because baseline is part of the response vector. As recommended by the CPMP (80), the model will also be adjusted for stratification variables of site, gender, and smoking status for improvement in precision. We will use an unstructured covariance to account for the correlation between repeated measurements, and we include a group-level random effect for intervention arm

patients, c_i, to account for the intra-class correlation between patients in the same prevention group. Similar procedures will be used to assess change through month 12 as a secondary analysis.

D.9.e. Aim 2 Analyses. Similar to the FRS, the secondary outcomes are all continuous and measured at baseline, month 6, and month 12. Analyses of these outcomes will thus proceed as describe above for FRS.

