D.9.f. Aim 3 Analyses. The analyses for Aim 3 will only include the intervention arm patients and will be exploratory in nature. The primary outcome for these analyses will be change in FRS from baseline to month 6. We will consider multiple ways of characterizing group cohesion, including: each individual's group cohesion score at the last group session; each individual's change in group cohesion from the first to the last group session; and, the mean group cohesion score at the last group session will be examined with a linear mixed-effects model, where additional predictors will include gender, smoking status, site, race, and age. A random effect for group membership will be included in the model to account for the intra-class correlation between patients in the same prevention group. Because the main predictors in these analyses are measured throughout the intervention, these analyses may be more impacted by drop-out or missed interim assessments than the Aim 1 and 2 analyses. We plan to use multiple imputation as the primary approach for handling missing data for the Aim 3 analyses.

D.9.e. Sample Size Calculations. The primary aim is to determine if there is a significant GPC vs usual care improvement in the mean FRS change from baseline to month 6. The clinically relevant mean FRS change is 2.0%. We assumed that FRS is normally distributed, and set the type-I error rate at α = 0.05 and the

type-II error rate at β = 0.20, representing power at 80% to detect significant differences. To take the intra-class correlation (ICC) among the group members in the GPC into consideration, we

applied the sample size procedures for group-randomized designs of Donner and Klar (88). Let *m* be the number of participants in each of the prevention coaching groups, and let ρ represent the ICC among the members of the group. In general, the minimum number of participants in each treatment arm is given by, $n = (Z_{1-\alpha/2} + Z_{1-\beta})^2 (2\sigma^2) [1 + (m-1)\rho] / (\mu_{GPC} - \mu_{UC})^2.$

Here, Z_p is the *p*-th percentile from the standard normal distribution, while μ_{GPC} and μ_{UC} is the anticipated mean change for the GPC and usual care arms, respectively. However, this formula is not quite right for this study – the control condition is usual care, and no ICC is anticipated among its members. As a result, the formula is modified to,

 $n = (Z1 - \alpha/2 + Z1 - \beta)^2 \{\sigma^2 + \sigma^2 [1 + (m - 1)\rho]\} / (\mu 1 - \mu 2)^2.$

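### Site, gender and smoking have the same effect at every visit in the printed primary model, so its precision and dropout claims rest on an unstated assumption

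*Combined protocol and SAP*

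**What the plan says.** The primary model in D.9.d is a constrained longitudinal model (cLDA) with unstructured covariance over visits. Its fixed part holds intervention-by-month terms, a month-12 term, and one coefficient each for site, gender and smoking (β4 to β6). None of these three is multiplied by month. The stated reason for them is: "the model will also be adjusted for stratification variables of site, gender, and smoking status for improvement in precision". D.4.a stratifies randomisation by site and gender only; that mismatch does not affect this point.

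Earlier in the same paragraph, comparing the cLDA with ANCOVA, D.9.d says "the two models are equivalent when there is no missing data".

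D.9.b says that the maximum-likelihood mixed model "implicitly accommodates missingness when missingness is due either to treatment, to prior outcome, or to other baseline covariates included in the model". It adds multiple imputation for missingness related to other measured factors, and sensitivity analyses for data missing not at random.

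D.9.e (Aim 2 Analyses) applies the same approach to the secondary outcomes. No section says that covariate effects are assumed equal across visits. D.9.d does not say whether smoking is the baseline or the visit value, although D.8.a measures every FRS component at each visit.

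**The concern.** A covariate with one coefficient adds the same amount at month 0 and month 6 and cancels from the modelled change. If the covariate does predict change, the model cannot use that information. The standard error is then larger than it needs to be, and conditioning on the covariate no longer fully protects against dropout related to it.

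Smoking is where equal effects are least plausible. It is an input to FRS, it is one of the goals named in D.5, and only smokers can lower FRS by quitting. Non-smokers enter through out-of-range blood pressure or lipids (D.3.a, D.3.c.i), which tend to drift back when re-measured. These mechanisms act differently in the two groups, so equal mean change would be a coincidence. What is at stake is some precision in the primary comparison and, under particular dropout patterns, a modest distortion of the estimate.

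**Working it through.** **Inputs from the plan** (D.9.e Sample Size Calculations): SD of change 6.3, baseline SD 14, correlation 0.9, ICC 0.03, group size 10, difference 2.0, two-sided α 0.05, power 80%, attrition 10%.

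**Assumptions not in the documents:** 40% smokers; D, the number of points by which mean FRS falls more in smokers than in non-smokers; the share R² of FRS variance explained by the covariate; the dropout patterns.

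**1. The plan's own figure.** n = (1.960 + 0.842)² × 39.69 × (1 + 1.27) / 2.0² = 176.8, so 177 per arm against the stated 180. Then 360 / 0.9 = 400, as stated. The SD of change checks as √(2 × 14² × 0.1) = 6.26. Covariates play no part in this calculation.

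**2. What the coding imposes.** Let g0 and g6 be the covariate's effects at months 0 and 6, and b the slope of month 6 on baseline (0.9 before adjustment, somewhat lower after).
- Covariate-adjusted ANCOVA: the coefficient given baseline is g6 − b·g0, freely estimated.
- Printed form: g6 = g0 = g, so the coefficient is forced to (1 − b)·g, about 0.1·g.

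The two agree only if g6 = g0.

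**3. When effects are equal (D = 0).** The variance of month 6 given baseline is 196 × (1 − 0.81) = 37.24 without the covariate. With it, the variance is 196(1 − R²) − (176.4 − 196R²)² / [196(1 − R²)]. This gives 37.02 at R² = 0.1, 35.93 at 0.4 and 34.30 at 0.6, a gain of 0.6% to 7.9%. In simulation, dropout related to the covariate was handled as well as with a month interaction (difference about 0.002 points).

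**4. Precision when effects differ.** The share of change variance left unexplained is 0.4 × 0.6 × D² / 39.69, and the standard error inflates by about 1/√(1 − share). The simulations used 400 patients, 10% missing at month 6, a month-6 main effect and no group effect.

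| D | Share | SE inflation, formula | SE inflation, simulated |
|---|---|---|---|
| 2 | 2.4% | 1.2% | 1.1% to 1.3% |
| 3 | 5.4% | 2.8% | 2.5% to 2.8% |
| 4 | 9.7% | 5.2% | 4.5% to 5.1% |

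At D = 0 the interaction cost nothing (SE 0.643 v 0.644).

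If smokers also start higher, the printed form can do worse than no adjustment. With complete data and D = 2, 4 and 6, its variance was 2.2%, 6.0% and 9.4% larger than unadjusted at R² = 0.2, and 1.9%, 8.6% and 15.8% larger at R² = 0.4. These R² values imply large baseline gaps of √(0.2 × 196 / 0.24) = 12.8 and √(0.4 × 196 / 0.24) = 18.1 points.

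**5. Dropout.** Take 25% dropout in GPC smokers, 5% in GPC non-smokers and 7% throughout usual care (10% overall). The smoker share among GPC patients seen at month 6 is 0.30 / (0.30 + 0.57) = 0.345; in usual care it stays at 0.40. The shift is about (0.40 − 0.345) × D = 0.055 × D, or 0.11, 0.17 and 0.22 for D = 2, 3 and 4.

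With a true effect of −2.0, simulated estimates under the printed form were about −1.91, −1.84 to −1.86 and −1.76. For D = −3 they were −2.15 to −2.18. With smoking-by-month added, all were within about 0.04 of −2.0. When dropout depended on the covariate equally in both arms, the distortion was 0.01 or less.

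**The case against.** A reader might infer that neither the precision gain nor the dropout protection is delivered. The documents do not support that: step 3 shows that both hold, the gain being small, when covariate effects are equal across visits.

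The sign and size of D are also open. Quitting lowers FRS in smokers, while drift back of blood pressure and lipids lowers it in non-smokers, so the two offset. D.3.c.iii excludes patients with a quit date or recent cessation-clinic enrolment, and D.5.g says most cessation-clinic patients fail to quit. D.3.c.iv re-measures blood pressure and lipids before randomisation, which limits later drift. D = 4 is twice the target effect. For gender, with about 10% women, D = 2 is only 0.1 × 0.9 × 4 / 39.69 = 0.9% of change variance.

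Nor is the trial shown to be underpowered. Ignoring the ICC, the planned standard error is √(2 × 39.69 / 180) = 0.664. With total change SD held at 6.3 and D from −5 to 3, the printed form gave 0.62 to 0.66.

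The bias needs a non-zero D and smoking-related dropout that differs by arm. D.9.b also offers multiple imputation and sensitivity analyses. The equivalence sentence precedes the covariate adjustment and concerns how time is coded, so it should not be read as a false claim about the adjusted model. The equation is visibly incomplete (no month-6 main effect), so it is weak evidence of a deliberate constraint.

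These points stand as limits on size and certainty. They do not remove the issue: no passage lets covariate effects differ by visit, multiple imputation is conditional and mainly aimed at factors outside the model, and nothing shows a downside to freeing the terms. If smoking were instead the visit value, the cancellation argument would not apply to it, but the model would then adjust for a post-randomisation input to its own outcome.

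**Conclusion.** The point holds in conditional form. As printed, modelled FRS change cannot vary by site, gender or smoking, so the precision purpose in D.9.d and the covariate part of the claim in D.9.b depend on equal covariate effects at every visit. This is unstated, and doubtful for smoking.

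With 40% smokers and D = 2 to 4, the standard error is about 1% to 5% larger than needed. Under the illustrative differential dropout the estimate shifts by about 0.055 × D, towards the null if smokers improve more and away from it if they improve less. The smoker share, D and the dropout pattern are all assumptions.

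The planned sample size is unaffected, and randomisation keeps the complete-data comparison unbiased. The adjusted cLDA matches a covariate-adjusted ANCOVA only when month-6 covariate effects are free.

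**What to change.** In D.9.d, add month6 × site, month6 × gender and month6 × smoking to the fixed effects, with the month-12 counterparts. State that smoking is the baseline value. Use the same terms for the Aim 2 outcomes.

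The cost is one line in the model statement and three fixed-effect parameters per follow-up visit. No new data or change in sample size is needed, and the extra terms cost no visible precision if covariate effects turn out to be equal. The adjusted model then agrees with a covariate-adjusted ANCOVA on complete data, and the claim in D.9.b no longer relies on equal effects over time for these three covariates.

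### The printed model has a month-12 treatment term but no group effect at month 12, so month-12 standard errors would be too small if it is used as printed and group clustering persists

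*Combined protocol and SAP*

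**What the plan says.** D.9.d (Primary Analysis) introduces one equation, by which FRS "change from baseline to month 6 will be examined with the following general linear mixed model". The outcome is defined "at *t*=month0, month6", yet the fixed part includes "\beta_2 month12 + \beta_3 int^* month12", that is, a month-12 time effect and a month-12 treatment effect. The only random term is the group effect multiplied by the intervention-by-month-6 indicator. Nothing random is attached to the intervention-by-month-12 term.

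The text below the equation describes the random effect more generally: "we include a group-level random effect for intervention arm" patients, to allow for correlation within a prevention group. It names no visit. An unstructured covariance handles repeated measurements.

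For month 12 the plan adds: "Similar procedures will be used to assess change through month 12 as a secondary analysis". For physical activity and diet, D.9.e (Aim 2 Analyses) says: "Analyses of these outcomes will thus proceed as describe above for FRS".

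**The concern.** An analyst who programs the equation as it stands would test the month-12 treatment coefficient from a model in which patients who shared a group for six months are independent of one another at month 12. The unstructured covariance does not repair this. It describes correlation between visits of one patient, not correlation between patients of one group.

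The plan itself treats the clustering as real. It sizes the trial with a design effect in the GPC arm and puts a group random effect in the Aim 3 model. Under D.5.c the same 10 patients meet each month with the same facilitators.

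At stake is the conclusion about persistence. D.4 presents follow-up to 12 months as the way to learn whether effects fade once contact ends. Intervals that are too narrow would make a lasting effect look better established than it is, for FRS and for the Aim 2 outcomes alike.

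**Working it through.** **Inputs from the sample size section.** SD of FRS change 6.3 points; difference to detect 2.0 points; ICC 0.03 (from earlier studies, no time point given); group size m = 10; clustering in the GPC arm only; 80% power. The authors "set the type-I error rate at α = 0.05" and use Z at 1 − α/2, so I work two-sided.

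**Reproducing the plan's figure.**
- Design effect in the GPC arm: 1 + 9 × 0.03 = 1.27.
- n per arm = (1.960 + 0.842)² × 6.3² × (1 + 1.27) / 2.0² = 7.849 × 39.69 × 2.27 / 4 = 176.8, so 177. The plan states 180, which is 1.7% higher.
- 360 / 0.9 = 400, as stated.
- SD check from the baseline SD of 14 and correlation of 0.9: 14 × √(2 × 0.1) = 6.26, about 6.3.

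The month-6 planning is therefore coherent and includes the clustering.

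**Leaving out the group effect at month 12.** With equal arms, the variance of the arm difference is proportional to 1 + [1 + (m − 1)ρ], where ρ is the month-12 ICC. A model without the month-12 group effect uses 1 + 1. So:
- true SE / model SE = √{[2 + (m − 1)ρ] / 2}
- actual two-sided error = 2 × [1 − Φ(1.96 / ratio)]

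At ρ = 0.03 and m = 10 the variance ratio is 2.27 / 2 = 1.135, and the SE ratio is 1.065. Since 1 / 1.065 = 0.939, the model SE is about 6% too small. The actual error is 2 × [1 − Φ(1.840)] = 6.6%. For scale, with SD 6.3 and 180 per arm, the SE would be reported as 6.3 × √(2 / 180) = 0.664 when it should be 6.3 × √(2.27 / 180) = 0.707.

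The documents give no month-12 ICC. The range below is assumed except for the plan's 0.03, which is itself assumed to carry over to month 12 (m = 10):

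| Month-12 ICC | True / model SE | SE too small by | Actual two-sided error |
|---|---|---|---|
| 0 | 1.000 | 0% | 5.0% |
| 0.01 | 1.022 | 2.2% | 5.5% |
| 0.03 | 1.065 | 6.1% | 6.6% |
| 0.05 | 1.107 | 9.7% | 7.7% |
| 0.10 | 1.204 | 17.0% | 10.4% |

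**Check in the longitudinal model.** The constrained model was evaluated by generalised least squares, with 18 groups of 10 against 180 controls. The group effect was fitted at month 6 only, while the true covariance also had one at month 12. The baseline to month-12 correlation was assumed to be 0.81 or 0.9. At ICC 0.03 the month-12 SE ratio is 1.069 to 1.072 and the error 6.7% to 6.8%. At 0.05 the ratio is 1.112 to 1.117 and the error 7.8% to 7.9%. The month-6 ratio is 1.000 throughout, so the primary comparison is untouched.

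**The case against.** The best defence is that the equation was never offered as the month-12 model. It is introduced for the month-6 change, declared for months 0 and 6, and used to test only the month-6 coefficient, for which a group effect at month 6 is what is needed. The text then runs straight from the purpose of the group effect to month 12: "to account for the intra-class correlation between patients in the same prevention group. Similar procedures will be used". Similar need not mean identical, and an ordinary reading would move the group effect along with the contrast. The equation is also loosely printed. It has no month-6 main effect, and the random effect carries subscript j in the equation and i in the text. It is thus weak evidence of a deliberate choice.

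Much of this stands. A reader might infer that the plan has decided to ignore clustering at month 12. The documents do not say so, and the prose points the other way. What the defence does not explain is why a model for months 0 and 6 contains two month-12 terms. As printed, the procedure nearest to hand for month 12 is to test the coefficient already in the equation, and there the group effect is absent. So the defence shows that equation and prose disagree, not that the specification is sound.

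The defence is also right that the size is uncertain. Groups stop meeting at month 6, so clustering may weaken. No ICC is given for physical activity or saturated fat. Smaller groups at month 12 would reduce the effect: with m = 8 and ICC 0.03, the SE is 4.9% too small and the error 6.2%.

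**Conclusion.** The point holds conditionally. The printed equation and the text on the group effect are inconsistent, and the month-12 random-effect structure is nowhere written out. The month-12 standard error would be understated if two things are true: the contrast is tested from the equation as printed, and within-group correlation for that outcome is above zero at month 12.

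At the plan's own ICC and group size the understatement is modest, about 6% on the standard error and 6.6% instead of 5% for the two-sided error. It vanishes at ICC 0 and grows with larger assumed values. A reader might go further and infer that every month-12 standard error in this trial is too small. The documents do not support that, because they give no ICC for that visit and none specific to the Aim 2 outcomes.

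Only secondary comparisons are affected. The plan should still be corrected, because persistence is a stated purpose of the second six months and the repair is simple.

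**What to change.** Rewrite the D.9.d equation for months 0, 6 and 12, and let the group effect act at both post-baseline visits: c_j6 × int × month6 + c_j12 × int × month12, with a 2×2 group-level covariance. State that this model supplies the month-12 FRS contrast and the Aim 2 contrasts.

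With about 20 GPC groups (200 patients in tens) and a small ICC, the 2×2 covariance may not converge. Name the fallback in advance: one shared c_j at both post-baseline visits. In the same edit, print the month-6 main effect and make the random-effect subscript consistent.

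The cost is one changed RANDOM statement, a corrected equation and a sentence of text. Month-12 intervals become slightly wider, by about 6.5% if the ICC there is 0.03. The month-6 test and the sample size need no change. If the authors intended this all along, the correction is clerical.
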